3.8 INNOVATION

Since 2006, the preclinical and clinical literature on the role of ghrelin and its receptor in AUD has been exponentially increasing. As such, targeting the ghrelin receptor system to treat AUD is a highly innovative approach. Recent translational work conducted by the PI and his team indicate a role of ghrelin in alcohol-seeking behaviors (Farokhnia et al., 2018; [name] et al., 2014). The first translational step taken by the PI and his team toward medication development has been to block GHS-R1a as a novel target to treat AUD. Safety and preliminary behavioral work have been conducted (Lee et al., 2018) and additional human work is ongoing under our current protocol, 16-DA-0080. The increasing knowledge of the ghrelin system has highlighted the potential role of the GOAT enzyme as a novel approach to target the ghrelin system. Therefore, this protocol is highly innovative as it represents the first attempt to test in humans the potential role of GOAT inhibition in AUD.

4 STUDY OBJECTIVES:

We propose to test the GOAT inhibitor GLWL-01 as a novel treatment for AUD. This will be a Phase 1b / 2a, proof-of-concept (early-signal) human laboratory study with GLWL-01 (450 mg b.i.d.).

GLWL-01 and matched placebo are provided by GLWL Research Inc. under a fully-executed NIH CRADA.

4.1 Primary outcome measures:

The co-primary aims will be to determine:

- 1) Whether the number of adverse events (AEs) experienced differ in the GLWL-01 condition, compared to placebo

PI Name: [name]., Ph.D., M.Sc.

Abbreviated Title: GOAT

Version Date: 09/25/2023

- 2) Whether GLWL-01, compared to placebo, reduces alcohol cue-elicited craving using a validated alcohol cue-reactivity procedure.

4.2 Secondary outcome measures:

The secondary aims will be to determine:

- a. Whether GLWL-01, compared to placebo, reduces food choices in a “virtual buffet” conducted in a virtual reality context.

Additional outcomes measures:

- b. We will also monitor behavioral assessments of pain, anxiety, depression, alcohol craving and withdrawal, and smoking.
- c. We will also monitor weight as well as food intake via a food intake

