When the participant returns to the CRU after the temporary leave, they will undergo the standard CRU participant search procedure and alcohol and drug screening. A positive BAC or urine drug screen that is positive for any of the following substances: benzodiazepines, barbiturates, cocaine metabolites, morphine, oxycodone, methadone, amphetamine, & buprenorphine may result in an extension of the wash-out window until they are able to provide a negative urine drug screen and or negative BAC or may

PI Name: [name]., Ph.D., M.Sc.

Abbreviated Title: GOAT

Version Date: 09/25/2023

result in termination of study participation and not moving on to the Stage 2 based on the clinical judgement of the PI and MAI. The urine drug screening is identical to the initial drug screen used in the screening procedure and it also includes testing for THC/cannabis however this is not an exclusion criterion nor will it result in termination study. Consistent with the initial drug screening, if cannabis use is detected it will be assessed and entered a covariate in the data analysis. After the inpatient stay, one outpatient follow-up visit in the clinic will be scheduled approximately a week after the discharge (the exact date may vary a little, based on the patient's schedule) to repeat the blood liver panel.

The following research procedures (1-3 listed below) will take place once in Stage 1 and once in Stage 2. These procedures will be the same for Stage 1 and Stage 2. Furthermore, beginning of study procedures may be delayed or participant may be withdrawn from the study for any clinical concerns (for example, clinically relevant severe alcohol withdrawal and/or any other clinical condition requirement immediate medical care).

These study procedures are similar to our ongoing protocol 16-DA-0080, therefore we will be able to compare the potential effects of GLWL-01 versus PF-5190457.

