7 STATISTICAL ANALYSIS

7.1 *Analysis of data/study outcomes*

Outcome data will be examined for homogeneity of variance, and if necessary transformed to meet this criterion. As this is a within-subjects design, repeated measures analysis of covariance (ANCOVA) will be used to analyze the primary outcome, with drug condition as the within-subjects factor. Similarly, for secondary outcome measures such as food choices, repeated measured ANCOVA will also be used.

Biomarkers and hormonal measurements, such as feeding-related peptides stress-related hormones and/or inflammatory markers (see Section G,1), will also be correlated with changes in primary and secondary outcomes to explore the relationship between hormonal responses of interest and behavioral changes. A probability level of 0.05 or lower will be considered significant.

Potential covariates will be evaluated such that covariates that significantly predict the outcome measure will be retained in the model. Negative affect, as measured by the POMS-2 and Symptom Checklist, and cannabis dependence, if present, will be entered as covariates of particular interest in analysis for primary and secondary outcome responses. Additional covariates include baseline characteristics, like age, race, years of education, alcohol drinking levels, ADS score, family history of alcoholism density and number of days of alcohol abstinence prior to enrollment.

7.2 *Power analysis*

We performed a power analysis for the primary outcome and it is consistent with: 1) our previous Phase 1b study (N = 12 completers) with PF-5190457, where the primary outcome was the number of AEs experienced differ in the drug condition, compared to placebo; and 2) effect sizes ($dz = 0.5$) of alcohol cue-reactivity studies for other medications like the FDA-approved naltrexone and other experimental compounds (George et al., 2008; Miranda et al., 2014; Monti et al., 1999, 2000). The goal will be to reach up to 34 completers. A sample size of 43 subjects will be needed: a) considering the following parameters: $dz = 0.5$, α err prob = .05, and power ($1 - \beta$ err prob) = .80 (see Table 1 for additional details); and b) considering an attrition rate of approximately 20%.

PI Name: [name]., Ph.D., M.Sc.

Abbreviated Title: GOAT

Version Date: 09/25/2023

Table 1: Power Analysis

t tests - Means: Difference between two dependent means (matched pairs)

[figure not shown]
Analysis: A priori: Compute required sample size

Input:

Tail(s)	= Two

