7.3 Accrual number

Consistent with the within-subject design and other human laboratory studies we and others have performed, we anticipate that approximately 20% of the enrolled participants may not complete the study. Therefore, we anticipate enrolling up to 43 participants in order to reach up to 34 completers.

PI Name: [name]., Ph.D., M.Sc.

Abbreviated Title: GOAT

Version Date: 09/25/2023

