12 DATA SAFETY AND MONITORING PLAN

The DSMP is consistent with the NIH policy 503 Specifically:

1. *Monitoring mechanism:* this study is monitored by the NIDA/NIAAA Addictions DSMB
2. *Frequency of the monitoring:* Initial DSMB review takes place before the study begins. Subsequent DSMB reviews take place after each 10 patients who have been exposed to study drug, unless otherwise recommended by the DSMB during the interim monitoring reviews
3. *Stop or change rules:* The following rules are followed:
 - 3a. Criteria for individual subject withdrawal:
 - A Serious Adverse Event (SAE) that is judged by the Investigators as being related to the study drug;
 - At the discretion of the PI and/or MAI and/or other health care provider involved in the study based on tolerability as well as adverse event (AE) severity, or self-reported symptoms and/or observed changes in patient's well-being as reported by health care providers including clinically significant changes in vital signs, weight/BMI, blood/urine laboratory values, etc.
 - ECG's (See Study Outline) will be monitored during each Stage as follows: ECG 12 lead with QTcF measurement (Fridericia equation) collected during STAGE 1 at Baseline (prior to dosing), Dosing Day 3, on Last Study Day, and on Washout Day -2 (or last Washout day if washout period extends beyond two days). ECG 12 lead with QTcF measurement (Fridericia equation) collected during STAGE 2 at Dosing Day 3 and Last Study Day. The ECG will be timed to coincide approximately with peak drug level. Specifically, according to the manufacturer data, Tmax ranged 1-6 hours at steady state in humans. Therefore, ECG will be done within 6 hours post study drug administration. If there is prolongation of the QTcF interval, either to >500 ms, or to > 60 ms over that on Day 1 ECG AND the absolute QTcF > 450 ms for males or >470 ms for females (**both criteria must be met**), ECG will be repeated and evaluated;
 - Significant non-compliance with protocol procedures or Investigator request;
 - Patient request.
4. *Advanced plans for any interim analyses and/or futility analyses.* There are no current plans for interim analyses and/or futility analyses

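### Run in its classical form, the planned within-subject ANCOVA of adverse-event number leaves out participants withdrawn before Stage 2, including those withdrawn because of an adverse event

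*Combined protocol and SAP*

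**What the plan says.** Section 4.1 lists two co-primary aims. The first is "Whether the number of adverse events (AEs) experienced differ in the GLWL-01 condition, compared to placebo"; the second is cue-elicited craving.

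For analysis, Section 7.1 states that "repeated measures analysis of covariance (ANCOVA) will be used to analyze the primary outcome, with drug condition as the within-subjects factor". It names no analysis population, no count model and no method for a participant who has data from one Stage only.

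Sizing is in terms of completers. Section 7.2 uses a matched-pairs t test, says "The goal will be to reach up to 34 completers", and supports the AE outcome by citing "our previous Phase 1b study (N = 12 completers) with PF-5190457, where the primary outcome was the number of AEs experienced". Section 7.3 adds that "we anticipate that approximately 20% of the enrolled participants may not complete the study".

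Section 12 (item 3a) lists the reasons for withdrawing an individual. One is "A Serious Adverse Event (SAE) that is judged by the Investigators as being related to the study drug"; another leaves withdrawal to clinical discretion "based on tolerability as well as adverse event (AE) severity". Section 5.4 also says that a "participant may be withdrawn from the study for any clinical concerns", although its example there is severe alcohol withdrawal or a need for immediate care.

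The missing-data paragraph in Section 5.4.7 is about collecting data and repeating a procedure. It does not say how a participant without a second Stage is analysed.

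**The concern.** A classical repeated measures ANCOVA compares the two conditions within each person, so it needs a value for both. A participant withdrawn in Stage 1 or wash-out has an AE count for one condition only and drops out of the comparison. Because AEs are themselves a reason for withdrawal, the outcome partly decides who is analysed. A drug-related serious AE that ends participation in Stage 1 would not enter the paired comparison at all.

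If AEs on GLWL-01 end participation more often than AEs on placebo, the events lost come mostly from the GLWL-01 side, and the estimated excess on a co-primary safety question is too small.

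**Working it through.** **1. The plan's own figure.** Inputs from Section 7.2 and Table 1: dz = 0.5, two-sided alpha 0.05, power 0.80. At n = 34 the noncentrality is 0.5 × √34 = 2.9155, df = 33 and critical t = 2.0345, giving power 0.8078 (n = 33 gives 0.7954). Then 34 / 0.8 = 42.5, rounded up to 43. All of this reproduces. It is a calculation for complete pairs, with an effect size from cue-reactivity studies rather than from AE counts.

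**2. How many could be left out.** 43 − 34 = 9 participants (20.9%). This is a ceiling: the plan does not say how many non-completers would leave before Stage 2, or how many because of AEs. As a check on the mechanics, a standard repeated measures ANOVA routine was given data in which one participant lacked the second condition. It stopped with an unbalanced-data error.

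**3. Size of the bias, by formula.** All rates here are assumptions. Let m be mean AEs per Stage and q the chance that an AE ends participation, with no between-person variation. Those who finish a Stage average m(1 − q) AEs in it.

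- Dropping before Stage 2 alone, orders weighted equally: (mG − mP) − 0.5(mG·qG − mP·qP).
- Only those who finish both Stages: mG(1 − qG) − mP(1 − qP).
- Expected Stage 1 withdrawals for AEs: 21.5(1 − e^(−mG·qG)) + 21.5(1 − e^(−mP·qP)).

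With mP = 0.5 and mG = 1.0 the true difference is 0.50. The last column is a simulation of 43 participants with alternating order, gamma between-person variance 0.5, AE-triggered stopping and no other dropout. It analyses every pair with any Stage 2 data.

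| qP / qG | Stage 1 AE withdrawals | Dropping alone | Finish both Stages | Simulated paired difference |
|---|---|---|---|---|
| 2% / 4% | 1.06 | 0.485 | 0.47 | about 0.47 |
| 5% / 10% | 2.58 | 0.4625 | 0.425 | about 0.42 |
| 10% / 20% | 4.95 | 0.425 | 0.35 | 0.355 |

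The simulated value lies below the dropping-alone formula for two reasons. Participants more prone to AEs leave first, and a Stage 2 cut short by an AE records fewer events.

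**4. What the last row represents.** In the 10% / 20% simulation, AEs cause 4.7 withdrawals in Stage 1 and 4.3 in Stage 2, leaving 34.1 completers. AEs therefore account for the whole of the planned attrition, so this row is an upper bound. Without the shortening of Stage 2 the paired difference is 0.419, so shortening explains (0.419 − 0.355) / (0.50 − 0.355) = 44% of the loss. Those participants stay in the comparison.

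**5. Other assumed rates.** Take 1.0 AE per Stage on placebo and 1.5 on GLWL-01, the same stopping chance per Stage 1 AE on both drugs (5%, 10%, 15%) and background withdrawal of 13%, 8% and 0%. Stage 2 is not shortened. Over 4,000 runs each:

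- Complete pairs give 0.468, 0.449 and 0.427, against 0.497, 0.501 and 0.498 if everyone were followed. The loss is 6%, 10% and 14%.
- Using all observed Stage data gives 0.495, 0.500 and 0.498.
- With equal AE rates there is essentially no bias (−0.007).
- With 20% withdrawal unrelated to AEs, the difference is 0.504 against 0.503. Power of the paired test falls from 52% to 43%, a loss of precision only.

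**6. An all-dosed count model.** Under the rates in step 3, with non-AE losses added to leave 34-35 completers, a gamma-Poisson model with drug, Stage and log days at risk gives a rate ratio of 2.03 at 5% / 10% and 1.99 at 10% / 20%, against a true 2.0. Power is not compared across methods, because they already differ with no AE-driven withdrawal (64% paired, 69% count model).

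**The case against.** A reader might infer that the plan requires complete pairs. It does not: nothing in Section 7 excludes one-Stage participants. Section 3.5 points partly the other way. The team's earlier within-subject alcohol study reports a mixed-effects model alongside a participant with no placebo data, and its imaging results have fractional degrees of freedom, consistent with mixed models. Such a model would keep a one-Stage participant. This stands, and it is why the point is limited to the classical form. But the present plan does not name such a model, and its sizing is entirely in completers.

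Section 7.1 also speaks of a single primary outcome. If that means craving alone, no ANCOVA drops anyone from the AE comparison, but a co-primary outcome then has no stated analysis. The same paragraph would repair that.

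A reader might take the 10% / 20% case as the expected bias. The documents do not support that. They name other routes out: patient request and non-compliance (Section 12), positive screens after leave (Sections 5.3 and 5.4) and leaving against medical advice (Section 10.7). Section 10.1 reports no clinically significant tolerability concern at a higher dose for up to 28 days.

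Two further inferences go too far. Section 10.1 reports one case of possibly related transaminitis during this study, but not that the participant was withdrawn or in which Stage, so it is not evidence of a lost event. Nor would safety oversight miss these events: AEs are checked daily in each Stage and reported to the DSMB, IRB and FDA. The gap is confined to the co-primary comparison.

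**Conclusion.** The point holds in a limited form. The only analysis named is a within-subject ANCOVA, with no analysis set and no rule for one-Stage participants. In its classical form it removes people withdrawn before Stage 2, some of whom may leave because of the outcome being compared. The bias is toward no harm provided that GLWL-01 AEs cause more withdrawals than placebo AEs.

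The size is modest at milder assumptions: a true difference of 0.50 AEs becomes about 0.47 to 0.42, a loss of roughly 6% to 16% (0.03/0.50 to 0.08/0.50), part of it from a shortened Stage 2. These figures rest on assumed AE rates and stopping shares. The plan should be corrected here, but this does not invalidate the trial.

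**What to change.** In Section 7.1, state the AE analysis separately:

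- Include every participant who received at least one dose, and keep unpaired Stages.
- Count AEs by the condition at onset. Use a mixed Poisson or negative binomial model with a participant effect, drug, Stage and log days at risk as offset. The offset also deals with a shortened Stage 2.
- List every AE that led to withdrawal or stopped dosing, by drug and Stage.
- If events are too few for a stable fit, report AEs per participant-day by condition with 95% confidence intervals, descriptively.

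The cost is about one paragraph and a little analyst time. It needs AE onset, dosing and withdrawal dates, with no new visits or samples, and can cover participants already enrolled if written before unblinding. The downside is that the model assumes withdrawal depends on recorded AEs, and it may be unstable with few events, hence the descriptive fallback.

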2013; Kraus et al., 2005). Together, these studies suggest that ghrelin levels are suppressed by acute alcohol intake and are increased during abstinence. The PI, [name], conducted a study that provided the first preliminary evidence of a significant positive correlation between blood ghrelin levels and the Obsessive-Compulsive Drinking Scale (OCDS) craving scores in active drinking alcoholic individuals (Addolorato et al., 2006), a finding also confirmed by another more recent study (Koopmann & von der Goltz et al., 2012). Other studies partially confirmed the relationship between blood ghrelin levels and alcohol craving in alcoholic individuals, albeit only in those with positive family history of alcoholism (Hillemacher et al., 2007) or in females (Wurst et al., 2007). [name] led the first longitudinal study of serum ghrelin levels in alcoholic patients over the course of 12 weeks treatment. Ghrelin concentrations were assessed at baseline (T0; after 72 hours abstinence), then repeatedly at 2 weeks (T1), 6 weeks (T2), and 12 weeks (T3); levels in abstinent patients were compared to those who did not remain abstinent during the 12-week treatment period. At baseline, blood ghrelin levels were significantly higher in the non-abstinent group ($p=0.035$) and there was a significant *group x time* interaction effect on ghrelin levels ($F=4.193$, $df=3$, $p=0.012$), [Figure 1]. These findings suggest that ghrelin level in early abstinence predicts later relapse. We also found a significant positive correlation between baseline ghrelin levels and craving during the 12-week period ([name] et al., 2012). In summary, consistent with the preclinical data, human studies show that higher ghrelin levels may be associated with higher craving and alcohol consumption, suggesting that ghrelin is a potential new pharmacological target for AUD. Moreover, a recent PET study (although in a different population of obese subjects) showing that peripheral ghrelin levels were inversely associated with the availability of DA type 2 receptor (D2R) in key reward processing areas such as the caudate, putamen, ventral striatum, amygdala, and temporal lobes, i.e., higher ghrelin levels were associated with lower D2R availability, presumably from increased DA release and receptor occupancy (Dunn et al., 2012). Notably, although only peripheral ghrelin levels were tested, circulating ghrelin may reach CNS targets directly by crossing the BBB (Chollet et al., 2009). Taken together, these results support the hypothesis that ghrelin may influence alcohol craving and consumption via the DA-related rewarding processing.

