The inpatient unit is operated and managed by Johns Hopkins Institute for Clinical and Translation Research (ICTR) and has standardized search procedures for any person staying on the unit. This search procedure is to prevent any items that are prohibited or illegal from entering the unit. If any prohibited items are found during the search procedure, the study team will be informed, and the items will be confiscated per ICTR policy. This will not result in the termination of study participation.

5.4 Overview:

Eligible participants will undergo Stages 1 and 2, where study drug (GLWL-01 or placebo) administration will be counterbalanced. A study drug wash-out window of at least 2 days will take place between Stage 1 and Stage 2. During each Stage, subjects will take the study drug twice a day (b.i.d.) for a minimum of 4 days to allow flexibility, maximize feasibility and minimize scheduling problems. At the end of each Stage, the last evening dose of the study medication will not be administered. As part of this study, subjects will be admitted to an inpatient facility (Clinical Research Unit (CRU)) on the Johns Hopkins Bayview Medical Center (referred to as either Bayview or JHBM) campus and will remain as inpatients for the duration of the two Stages and the wash-out window for an inpatient stay of approximately 14 days. We allow some flexibility to accommodate patient and CRU scheduling needs with a maximum possible 21-day length of total number of inpatient stays allowed. As for many other NIDA clinical protocols, study procedures take place either in the Bayview CRU or the NIDA IRP Biomedical Research Center (BRC) building which are both on the Bayview campus in Baltimore, MD. Participants may only leave the CRU during the wash-out window for personal emergencies and extenuating circumstances pending the approval of the PI, MAI or other covering health care provider who will evaluate the pass request and determine whether the pass may be granted. Participants on approved leave during washout do not receive remuneration while on leave and the total number of days on leave do not count toward the 21-day ceiling of stay in our clinical facilities during their participation in this study.

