Effect size dz	= 0.5
α err prob	= 0.05
Power (1- β err prob)	= 0.8

Output:

Noncentrality parameter δ	= 2.915476
Critical t	= 2.034515
Df	= 33
Total sample size	= 34
Actual power	= 0.807778

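### Section 7.1's hormone–outcome correlation has no term for treatment order; if drug-minus-placebo changes are pooled over both orders, average stage drift in both variables induces a correlation, even with balanced orders

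*Combined protocol and SAP*

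**What the plan says.** Section 7.1 (Analysis of data/study outcomes) analyses the outcomes by repeated measures ANCOVA with drug condition as the within-subjects factor. It then says that biomarkers and hormonal measurements "will also be correlated with changes in primary and secondary outcomes to explore the relationship between hormonal responses of interest and behavioral changes". The next sentence sets the threshold: "A probability level of 0.05 or lower will be considered significant". No formula for the change is given. Stage, period, order and sequence appear neither in the model nor in the list of covariates. The listed covariate for days abstinent is measured before enrolment, so each person has one value and it cannot describe movement between stages.

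Section 5.2 randomises participants to GLWL-01 then placebo, or the reverse. Section 5.4 puts both stages into one inpatient stay of about 14 days, in which participants "will remain as inpatients for the duration of the two Stages and the wash-out window". On ghrelin, section 3.5 concludes that "these studies suggest that ghrelin levels are suppressed by acute alcohol intake and are increased during abstinence".

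**The concern.** A drug-minus-placebo change is Stage 1 minus Stage 2 for people who take GLWL-01 first, and Stage 2 minus Stage 1 for the others. A general time trend over the stay therefore enters the change with opposite signs in the two orders. In the average over balanced orders the trend cancels. In a correlation between two such changes it does not, because both changes flip sign together and the product of the two trends survives.

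This is the only hormone–behaviour analysis that section 7 states, in a proof-of-concept trial whose rationale is that ghrelin signalling drives craving. Section 3.5 already reports positive ghrelin–craving correlations. An artefact in that direction would look like confirmation, and one in the other direction could hide a real link. Drift in the hormone is plausible from the plan's own background: ghrelin is described as rising in abstinence, and both stages fall within one inpatient stay.

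**Working it through.** **The plan's own figure.** Section 7.2 uses a two-sided paired t-test with dz = 0.5, alpha 0.05 and power 0.80. At n = 34 the noncentrality is 0.5 × √34 = 2.9155, the critical t on 33 df is 2.0345 and the power is 0.8078. This matches "Actual power = 0.807778". With 20% attrition, 34 / 0.80 = 42.5, rounded up to 43. Both figures reproduce, and 34 is the n used below.

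**Inputs.**
- n = 34 completers (section 7.2), split 17:17 between orders (assumed perfect balance).
- Two-sided 0.05 test of a Pearson correlation. The level is from section 7.1; two-sidedness is assumed. The critical |r| at n = 34 is 0.339.
- Both variables taken as GLWL-01 minus placebo (a reading, since 7.1 does not define the change).
- Drift of 0 to 1 SD of the within-person difference (assumed; the documents give no value).

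**Algebra.** Let s = −1 for GLWL-01 first and +1 for placebo first. For hormone h and craving c:

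D_h = τ_h + s·δ_h + e_h and D_c = τ_c + s·δ_c + e_c,

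with e_h and e_c independent and of SD 1, so there is no true link.

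- Mean: with 17:17, s averages 0, so the mean of D_c is τ_c and drift drops out.
- Covariance: s² = 1, so Cov(D_h, D_c) = δ_h·δ_c.
- Variances: 1 + δ_h² and 1 + δ_c².
- Induced correlation: r = δ_h·δ_c / √((1 + δ_h²)(1 + δ_c²)).

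For δ_h = δ_c = 0.5, r = 0.25 / 1.25 = 0.20. For 1.0, r = 1 / 2 = 0.50.

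**Simulation** (100,000 trials per setting). The adjusted test centres both changes within order and uses 31 df.

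| Drift in hormone, craving (SD) | r from formula | False positives, pooled | False positives, order-adjusted |
|---|---|---|---|
| 0, 0 | 0.00 | 5.1% | 5.1% |
| 0.2, 0.2 | 0.04 | 5.6% | 5.0% |
| 0.3, 0.3 | 0.08 | 7.4% | 5.0% |
| 0.5, 0.5 | 0.20 | 21% | 5.1% |
| 0.8, 0.8 | 0.39 | 69% | 5.1% |
| 1.0, 1.0 | 0.50 | 92% | 5.0% |
| 0.5, −0.5 | −0.20 | 21% | 5.0% |
| 0.5, 0 | 0.00 | 5.1% | 5.0% |

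With a true mean drug effect set at −0.50, the simulated mean contrast stayed at −0.50 in every balanced setting. Balance protects the mean but not the correlation. At 20:14 orders and drift 0.5 in both, the pooled test rejects in 20% of trials and the adjusted test in 5.1%.

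**Other readings of the variables.**
- On-drug hormone level against drug-minus-placebo craving change: r = 0.11 and 9.4% false positives at drift 0.5; r = 0.32 and 47% at 1.0 (hormone drift in SDs of that level).
- Both variables taken within one drug condition: the orders then sit only half a drift either side of their mean, so for equal drift d, r = (d²/4) / (1 + d²/4). This is 0.06 at 0.5 and 0.20 at 1.0, with about 6% and 21% false positives (d in SDs of the level).
- Hormone as a baseline level or a two-stage mean: r = 0 and about 5%.

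**Limit of the adjustment.** If drift varies between people (mean 0.5, SD 0.5 in each variable) and a person's hormone and craving drifts correlate at 0.5 to 0.8, the order-adjusted test still rejects in about 9% to 14% of trials. These settings are assumptions.

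**The case against.** Neither the pooling nor the drug-minus-placebo form is stated; both are inferred from the absence of an order term and from the within-subject design. Section 7.1 speaks of hormonal measurements on one side and changes on the other. The group's earlier cue-reactivity study, described in section 3.5, related ghrelin level to the rise in urge within a session, and section 5.4.1 makes the water trial a baseline in the same way. If that is what 7.1 means, and the correlation is run within one drug condition, the artefact is much smaller; subtracting the water response could also cancel drift common to both cues. This stands, and it is why the point is conditional.

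Both variables must drift. The background cited concerns ghrelin only, gives no size for stages a few days apart, and nothing in it shows drift in cue-elicited craving. Some participants may be abstinent or detoxified before entry, so part of the ghrelin rise may precede Stage 1. This also stands: the 0.8 and 1.0 SD rows show how the bias grows and do not predict it.

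A reader might infer that any drift invalidates the analysis, that the drug effect on craving is biased too, or that adjusting for order solves the problem entirely. The documents and calculations support none of these. Small drift does almost nothing, the balanced mean contrast is untouched, and the adjustment removes average drift only. Nor can a count of planned tests be read from the markers named in section 6.1, which is an open-ended list for future use.

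What remains is that the plain correlation has no safeguard against a known artefact, and the information needed to remove its main part is already recorded.

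**Conclusion.** The concern holds conditionally. If both variables are GLWL-01 minus placebo and are correlated over both orders without adjustment, average drift in both biases the correlation despite counterbalancing. The bias matters from roughly 0.5 SD in both (21% false positives against a nominal 5%). Its direction follows the signs of the two drifts.

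The result rests on three things the documents do not settle: how the change is defined, whether the orders are pooled, and how large the drifts are. The primary comparisons and the sample size of 34 completers from 43 enrolled are unaffected. This is an inexpensive improvement to an exploratory analysis and does not challenge the trial's main conclusions.

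**What to change.** In section 7.1, define the hormone change and the outcome change both as GLWL-01 minus placebo. State that they will be correlated adjusted for randomised treatment order, either as a partial correlation given sequence or after subtracting the sequence mean from both changes. Report the results as exploratory estimates with confidence intervals, without a significance label at 0.05.

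The cost is one degree of freedom (31 instead of 32 at n = 34) and a sentence or two of text, with no new data, visits or participants. The text should acknowledge that this removes average drift only: individual drifts that are correlated between hormone and outcome would remain.
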